8.3 Vinblastine

8.3.1 Other names.

Velban, vinblastine sulfate, vincaleukoblastine, VLB, Velsar, Alkaban AQ.

8.3.2 Classification

Vinca alkaloid (tubulin inhibitor).

8.3.3 Mode of Action.

Vinblastine binds to tubulin, a protein that forms microtubules, thus interfering with spindle formation during metaphase and causing cessation of cellular mitosis.

54

8.3.4 Storage and stability.

Drug vials are stored in the refrigerator. Reconstituted vinblastine, 1 mg/ml, is stable for 30 days in the refrigerator. Further diluted to a concentration of 0.01 mg/ml in normal saline or 5% dextrose, vinblastine is stable for 24 and 72 hours, respectively, at room temperature.

8.3.5 Dose specifics

Patients will receive Velban intravenously at a dose of 6 mg/m2 on days 1 and 15 of each AVD chemotherapy cycle. A cycle will be repeated every 28 days. Use actual weight to calculate body surface area and doses. See section 5.3.3 regarding dose modifications (toxicity-related).

8.3.6 Preparation.

The 10 mg vial is reconstituted with 10 ml of bacteriostatic normal saline, yielding a concentration of 1 mg/ml. Doses for continuous infusion may be further diluted with 50 ml or more of normal saline or 5% dextrose in water.

8.3.7 Administration.

Intravenously as a bolus injection.

8.3.8 Incompatibilities.

Furosemide, heparin; Infusaid pumps.

Compatibilities. Vinblastine is physically stable in normal saline solutions for at least 5 days, alone or mixed with doxorubicin, at 8, 25, and 32°C. Vinblastine is also compatible in solution with metoclopramide and bleomycin.

8.3.9 Availability.

Vinblastine is commercially available in 10 mg vials, as a lyophilized powder and as a 1 mg/ml solution.

8.3.10 Side effects.

Hematologic: Leukopenia, thrombocytopenia, anemia. Dermatologic: Alopecia, epilation; skin and soft tissue damage if extravasated (the manufacturer recommends subcutaneous injection of hyaluronidase and application of heat to help disperse the drug); rash, photosensitivity. Gastrointestinal: Nausea, vomiting (preventable); constipation (see neurological side effects); abdominal pain (cramps), anorexia, diarrhea, mucositis, gastrointestinal hemorrhage. Neurologic: Peripheral neuropathy (loss of deep tendon reflexes, paresthesias, paralysis); autonomic neuropathy (constipation, paralytic ileus, urinary retention, orthostasis); vocal cord paralysis; myalgias; Raynaud's phenomenon; headache, seizures, depression, dizziness, malaise; may be enhanced by concomitant use of interferon. Pulmonary; Bronchospasm (acute shortness of breath), more common when administered with mitomycin; pulmonary edema. Other: Severe pain in the jaw, pharynx, bones, back or limbs following injection; syndrome of inappropriate antidiuretic hormone (SIADH); fever; ischemic cardiotoxicity; enhanced interferon toxicity.

8.3.11 Nursing/patient implications.

Premedicate with antiemetics as needed. Administer by slow IV push. Vesica—t - do not extravasate. Refer to extravasation protocol if inadvertent infiltration occurs. Assess for neurotoxicity. Assess for constipation. Monitor CBC and platelet count.

8.4 Dacarbazine

8.4.1 Other names

DTIC, DTIC-D'me,, DIC, imidazole carboxamide, dimethyl triazeno imidazole carboxamide.

8.4.2 Classification.

Alkylating agent.

8.4.3 Mode of Action.

Activity may be the result of at least 3 mechanisms: 1) alkylation; 2) antimetabolite activity as a purine precursor; and 3) interaction with sulfhydryl (SH) groups in proteins. Dacarbazine appears to be more active in G2 phase but is not particularly cell cycle phase specific.

8.4.4 Storage and stability.

Store vials under refrigeration and protected from light. In solution, dacarbazine is stable for 96 hours if refrigerated and protected from light, 24 hours if not refrigerated but protected from light. When further diluted in 500 ml D5W or NS, it is stable for 24 hours if refrigerated, and 8 hours at room temperature and protected from light. Photodegradation: The manufacturer of dacarbazine states that the drug does not decompose when left at room temperature under normal lighting conditions for eight hours.

NOTE: A change in color of solution from pale yellow to pink is indicative of decomposition of the drug.

8.4.5 Dose specifics.

Patients will receive Dacarbazine intravenously at a dose of 375 mg/m2 on days 1 and 15 of each cycle of AVD chemotherapy. Cycles will be repeated every 28 days. Use actual weight to calculate body surface area and doses. See section 5.3.3 regarding dose modifications (toxicity- related).

8.4.6 Preparation.

Dilute the 100, 200, and 500 mg vials with 9.9, 19.7, and 49.5 ml of sterile water, respectively, resulting in a concentration of 10 mg/ml. Protect the drug from direct light. Do not freeze. Discard if solution turns pink/red. The drug can be further diluted in 50-500 ml of 5% dextrose or normal saline.

8.4.7 Administration.

Usually administered by intravenous infusion over 30 minutes or longer; has also been given IV push.

8.4.8 Incompatibilities.

Metabolism of dacarbazine may be induced by phenytoin or phenobarbital. Toxicity may be enhanced if given concomitantly with allopurinol, azathioprine, or mercaptopurine. Dacarbazine is physically incompatible with hydrocortisone sodium succinate and heparin.

8.4.9 Side effects.

Central nervous system: Infusion-site pain; Dermatologic: Alopecia Gastrointestinal: Nausea and vomiting (>90%), anorexia; Hematologic & oncologic: Bone marrow depression (onset: 5 to 7 days; nadir: 7 to 10 days; recovery: 21 to 28 days), leukopenia, thrombocytopenia <1% (Limited to important or life-threatening): Anaphylaxis, anemia, diarrhea, dysgeusia, eosinophilia, erythema, facial flushing, facial paresthesia, flu-like symptoms

(fever, myalgia, malaise), hepatic necrosis, increased liver enzymes (transient), paresthesia, renal function test abnormality, skin photosensitivity, skin rash, urticaria, venous obstruction (hepatic vein)

8.4.10 Nursing implications

Premedicate with antiemetics as agent is highly emetogenic. Infuse over 15-60 minutes. Irritant- rapid infusion may cause severe venous irritation. Assess for allergic reactions. Monitor CBC and platelet count.

8.4.11 Availability.

Commercially available in vials containing 100 mg, 200 mg, or 500 mg of lyophilized drug.

9.0 CORRELATIVES/SPECIAL STUDIES

Several correlative studies are included in the clinical trial protocol. Expression of PD-1 and PD-L1 has been identified on malignant cells and cells of the tumor microenvironment in hematologic malignancies including Hodgkin's lymphoma⁴⁸. We will analyze the previously obtained biopsy specimens from patients' diagnostic samples (if available) to determine PD-1 and PD-L1 expression. An optional biopsy specimen will also be collected 2-4 weeks after the first dose of pembrolizumab for patients who provide consent. Expression of both PD-1 and PD-L1 has been correlated with responses following anti-PD-1 therapy. For HL, mutations at chromosome 9p24.1 led to amplification of gene expression of PD-L1 and PD-L2³¹. We will perform FISH testing to identify mutations in chromosome 9p24.1 and attempt to correlate with both PD-L1 expression as well as clinical outcomes. Prior studies using anti-PD-1 blockade have shown alterations in the Tlymphocytes subsets following therapy⁴³. The correlative investigations will determine lymphocyte subset changes during treatment with pembrolizumab. Levels of serum markers associated with inflammatory and immune response will include TNF-α, IFN-y, IL-2, IL-6, IL-7, and galectin-1. Correlation of these biomarkers will be investigated as potential measures to determine response to therapy. More recently the use of an ELISA assay for soluble PD-L1 (sPD-L1) has emerged as a potential biomarker for response to PD-1 blockade in DLBCL⁴⁹. The role of sPD-L1 in HL is unclear and this will be part of our correlative investigations.

9.1 Diagnostic Biopsy – Specimen Procurement & Shipping

Tissue will be obtained for correlative studies from the diagnostic biopsy performed at baseline, if available. Archival tissue will be approved if appropriately preserved in paraffin embedded block, and if the specimen is deemed adequate for correlative studies by the onsite pathologist. An optional biopsy specimen will also be collected 2-4 weeks after the first dose of pembrolizumab for patients who provide consent. The biopsy samples for each patient will be obtained for PD-1 pathway marker analysis and chromosome 9p24.1 alterations. For each biopsy specimen, either 10 unstained slides (5 microns) or a paraffin-embedded block will be submitted for :

- o Immunohistochemical (IHC) analysis of PD-1 and PD-L1 expression.
- A block section is also required to complete FISH analysis for alterations at chromosome 9p24.1.
 See separate lab manual for details on processing and shipping.

9.2 Biopsy Specimen Analysis

Immunohistochemical stains for PD-1 and PD-L1 will be performed by the Northwestern PathCore facility with proper controls. We will also perform IHC for CD3 and CD20 for identification of tumor cells and the tumor microenvironment. Samples will be reported as "present" or "absence" of marker expression. Expression will be quantified by percentage of cells with differentiation between malignant cell expression and/or tumor microenvironment expression. We will consider >20% as "positive" for PD-1 or PD-L1 expression.

FISH

Fluorescence in situ hybridization (FISH) will be performed by the Northwestern pathology department on tissue sections to assess alterations of chromosome 9p24.1. Chromosomal alterations will be characterized as amplification, copy gain, polysomy, or normal copy number (disomy). The bacterial artificial chromosome probes (CHORI; www.chori.org) RP11-599H2O, which maps to 9p24.1 and includes CD274 (encoding PD-L1, labeled with Spectrum Orange), and RP11-635N21, which also maps to 9p24.1 and includes PDCD1LG2 (encoding PD-L2, labeled with Spectrum Green), will be cohybridized. A control centromeric probe, Spectrum Aqua—labeled CEP9 (Abbott Molecular) that maps to 9p11-q11, will be used. An additional probe, Spectrum-Greenlabeled RP11-6010G2, which maps upstreatm of PDCD1LG2, will be used to confirm a possible chromosomal translocation.

Double Immunohistochemistry Staining

Slides will be double stained for the presence of PD-L1 and PAX5 (24/Pax-5;BD Biosciences, San Jose, CA) as well as PD-L2 clone and pSTAT3 (D3A7; Cell Signaling, Danvers, MA). These stains will be performed with an automated staining system (Bond III; Leica Biosystems, Buffalo Grove, IL). Stained slides will be scored by an expert hematopathologist for average percentage of positive cells and intensity of staining on a scale (1-3+).

9.3 Peripheral Blood Correlatives

9.3.1 Flow Cytometry – Sample Procurement

Lymphocyte subsets will be evaluated by flow cytometry on peripheral blood obtained at specified time points through the treatment period. See separate lab manual for collection and processing details.

9.3.3 Flow Cytometry Analysis

Flow cytometry analysis will include the following surface markers: CCR7, CD3, CD4, CD8, CD14, CD16, CD20, CD25, CD45RO, CD56, CD57, CD62L, CD107a, CD127, FoxP3, B7-H1 (PD-L1), B7-DC (PD-L2), HLADR, and PD-1. The following intracellular markers will be evaluated: TIA1, granzyme, perforin. We will complete an 8-10 color flow cytometry analysis to properly group biomarkers for determination of specific lymphocyte populations. Two specific lymphocyte populations will be evaluated as the primary endpoint and include CD4+CD25+PD-L1+ T lymphocytes and CD4+CD62L+CD127+ T lymphocytes. Further groupings of marker expression will be performed to best identify activated T-cell and NK-cell populations, cytotoxic T-cells, monocyte populations, and lymphocyte populations with PD-1 or PD-L1 expression

9.3.4 Correlative Inflammatory and Immune Markers

Peripheral blood samples will be obtained at specified time points per the treatment protocol. Serum marker evaluations will include TNF- α , IFN- γ , IL-2, IL-6, IL-7, and galectin-1. See separate lab manual for collection and processing details. For each specified time point, peripheral blood sampling will require an 8.5mL SST tube. Samples will be spun, frozen and stored appropriately until testing is performed. Values will be reported with units and reference ranges based on the respective commercially available tests. All patient samples will be stored until final tissue acquisition, following by batch analysis. Blood fractions, including serum and PBMCs will be stored for analysis Samples will be stored until study completion

9.3.4 Thymus and Activation-Regulated Chemokine/CCL17 (TARC)

For the CCL17 ELISA (https://www.rndsystems.com/products/human-ccl17-tarc-quantikine-elisa-kit_ddn00.), peripheral blood samples will be obtained at specified time points per the treatment protocol along with the inflammatory

markers. See separate lab manual for collection and processing details.

Soluble PDL-1 9.3.5

Peripheral blood samples will be obtained at specified time points per the treatment protocol. See separate lab manual for collection and processing

9.4 Specimen Banking

Patient samples collected for this study will be retained at Robert H Lurie Cancer Center of Northwestern University Pathology Core Facility. Specimens will be stored indefinitely or until they are used up. If future use is denied or withdrawn by the patient, best efforts will be made to stop any additional studies and to destroy the specimens.

[name] will be responsible for reviewing and approving requests for clinical specimen from potential research collaborators outside of Northwestern University. Collaborators will be required to complete an agreement (a Material Transfer Agreement or recharge agreement) that states specimens will only be released for use in disclosed research. Any data obtained from the use of clinical specimen will be the property of Northwestern University for publication and any licensing agreement will be strictly adhered to.

The following information obtained from the subject's medical record may be provided to research collaborators when specimens are made available:

- Diagnosis
- Collection time in relation to study treatment
- Clinical outcome if available
- Demographic data

STATISTICAL CONSIDERATIONS 10.0

This is a Phase II trial to estimate the clinical response (complete response rate) following administration of pembrolizumab with AVD chemotherapy for patients with de novo Hodgkin's lymphoma. We will also describe toxicity and gather preliminary data about efficacy (EFS and OS). Biologic correlates will be studied in an exploratory fashion.

10.1 **Evaluability**

To be evaluable for inclusion in the analysis to address the primary objective, patients must:

- have received at least one dose of pembrolizumab
- have a FDG-PET/CT scan following cycle #3 of pembrolizumab (PET#2)

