4.6.3 Subject Withdrawal/Discontinuation Criteria from Treatment and/or Overall Study

Subjects may withdraw consent at any time for any reason or be dropped from the trial at the discretion of the investigator should any untoward effect occur. In addition, a subject may be withdrawn if enrollment into the trial is inappropriate, the trial plan is violated, or for administrative and/or other safety reasons. Specific details regarding discontinuation or withdrawal are provided in Table 4.1.

A subject must be discontinued from the trial for any of the following reasons:

- Patient voluntarily withdraws from treatment (follow-up permitted)
- The subject or legal representative (such as a parent or legal guardian) withdraws consent (no follow-up permitted).
- Confirmed radiographic disease progression
- Note: For unconfirmed radiographic disease progression, please see Section 5.1.6
- Unacceptable toxicity/adverse experiences as described in Section 4.4
- Intercurrent illness that prevents further administration of treatment
- Investigator's decision to withdraw the subject (i.e. continuation not in the patient's best interest)
- The subject has a confirmed positive serum pregnancy test
- Patient develops a second malignancy that requires treatment which would interfere with this study
- Noncompliance or inability to comply with trial treatment or procedure requirements
- The subject is lost to follow-up
- Administrative reasons

The End of Treatment and Follow-up visit procedures are listed in Section 5 (Protocol Flow Chart). After the end of treatment, each subject will be followed for 30 days for adverse event monitoring (serious adverse events will be collected for 90 days after the end of treatment as. Subjects who discontinue for reasons other than progressive disease will have post-treatment follow-up for disease status until disease progression, initiating a non-study cancer treatment, withdrawing consent or becoming lost to follow-up. After documented disease progression each subject will be followed by telephone for overall survival until death, withdrawal of consent, or the end of the study, whichever occurs first.

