4.6.4 Patient Replacement

Any patient who is registered to the study and then withdrawn without receiving any study treatment may be replaced. Any patient who completes fewer than 2 total cycles of therapy and is withdrawn for any reason except PD or toxicity will still be considered evaluable for toxicity endpoints; however, for the purpose of efficacy endpoints, another patient may be added; if the maximum accrual of 30 is reached without achieving the 26 evaluable necessary for evaluation of efficacy, an increase to the accrual goal may be requested with the approval of the Data and Safety Monitoring Committee (DSMC) at Northwestern University. No follow-up is required for patients that withdrew and did not receive any study treatment.

37

Initial Version date: March 10th, 2017

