6.4 Endpoint assessment

6.4.1 Primary Endpoint

Our primary endpoint is to assess rate of complete response following pembrolizumab alone on FDG-PET (PET#2). This will be performed following three cycles of pembrolizumab on week 10. The scheduling window is day 64 +/-3 days. Negative PET is defined as Deauville score of 1-3 as assessed by central review. Patients will be considered evaluable for this endpoint if they have received at least one dose of pembrolizumab.

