10.2 Sample Size and Accrual

This is a Phase II study in which the primary aim will be to determine the complete response rate to up front pembrolizumab. The treatment paradigm of this trial will be considered worthy of further evaluation if at least 40% of patients achieve CR at PET#2 (defined as Deauville 1-3).

The target sample size for the primary response analysis is 26 patients, with 4 additional patients to be accrued to account for dropout, so that the total target sample size is 30 patients in order to increase the CR rate to single agent pembrolizumab from the baseline level of 20% in relapsed/refractory patients, to 40% with a power of 84% at an alpha level of 10%. For the analysis of complete response by PET, a single arm single stage Bayesian design with 26 patients may also be used. Response is defined as a Deauville score of 1-3 after the initial treatment with pembrolizumab alone. The posterior probability of a response rate being greater than 50% will be calculated using a non-informative prior

distribution. With 26 patients, the following table gives this posterior probability for an observed number of responses.

Observed number of responses/26: 11 12 13 14 15 Probability that response rate > 40%: 0.61 0.75 0.86 0.92 0.96

Therefore, to be more than 80% sure that the response rate exceeds 40%, at least 13 of 26 responses would need to be observed in the total population. After PET#3, patients will be analyzed as a total population as well as by age cohort for response rate, PFS, and OS.

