10.3 Data Analyses Plans

10.3.1 Analytic Plan for Primary Objective

To assess the primary objective of response rate following PET (2) performed after 3 doses of pembrolizumab, we will assess PET response using the 5 point Deauville criteria. Patients with a Deauville score of 1-3 will be considered a complete response. Patients will be evaluable for response assessment if they have received at least one dose of pembrolizumab. Response will be determined in all patients after induction (PET # 2) and after chemotherapy (PET # 3) using a proportion and an exact binomial 95% confidence interval. It will be observed whether 50% is in the confidence interval. Continuous futility monitoring will occur using the method of Lee & Liu. ⁵⁰ While this method may be used to identify a futile level of response after each patient, it will begin monitoring after 10 patients. Futility will be indicated if at most 1/10, 3/15 or 5/20 evaluable patients have a response, assuming 26 total evaluable patients will be observed. For these calculations, futility means that the posterior probability that the response rate exceeds 50% is less than 10%.

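### Section 10.1 requires a PET#2 scan for the primary analysis, but 6.4.1 and 10.3.1 require only one dose. If unscanned patients count as non-CR, the 10.1 set gives a CR rate that is the same or higher.

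*Combined protocol and SAP*

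**What the plan says.** Three passages define who counts for the primary endpoint, CR at PET#2 (Deauville 1-3).

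- **Section 10.1** sets two conditions for the analysis of the primary objective: at least one dose of pembrolizumab, and that patients "have a FDG-PET/CT scan following cycle #3 of pembrolizumab (PET#2".
- **Section 6.4.1** sets one: "Patients will be considered evaluable for this endpoint if they have received at least one dose of pembrolizumab".
- **Section 10.3.1** also sets one: "Patients will be evaluable for response assessment if they have received at least one dose of pembrolizumab".

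Section 4.6.4 bears on the same set. It covers "Any patient who completes fewer than 2 total cycles of therapy and is withdrawn for any reason except PD or toxicity". Such a patient stays evaluable for toxicity, but "for the purpose of efficacy endpoints, another patient may be added". The exception for PD and toxicity implies that early failures of those kinds are kept for efficacy.

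The decision rules are in 10.2 and 10.3.1. The regimen is "considered worthy of further evaluation if at least 40% of patients achieve CR at PET#2". A "single arm single stage Bayesian design with 26 patients may also be used", and for it 10.2 asks for at least 13 responses in 26 in order to be more than 80% sure that the rate exceeds 40%. The futility counts in 10.3.1 are also stated in evaluable patients. The target is 26 evaluable patients, with 4 more enrolled to cover dropout (10.2) or unevaluable patients (Study Summary).

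**The concern.** PET#2 is scheduled for day 64 ± 3. Section 4.6.3 opens its list with "A subject must be discontinued from the trial for any of the following reasons", and the list includes confirmed progression and unacceptable toxicity. Nothing there requires PET#2 first, so a dosed patient can leave without the scan.

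Under 10.1 that patient is outside the primary analysis. Under 6.4.1 and 10.3.1 the patient is inside it, but no score is defined for a missing PET#2. Patients who leave for progression or toxicity are mostly treatment failures, so excluding them is not neutral. At stake is the denominator of the primary endpoint in a single-arm trial of 26 patients. If the choice is left open, it could be made after the results are known.

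**Working it through.** **Inputs.** From 10.2: 26 evaluable patients, 4 extra, success at an observed CR rate of at least 40%, and an optional rule of posterior P(rate > 40%) above 0.80 with a non-informative prior. Assumed: a Beta(1,1) prior; k dosed patients without PET#2, each scored as non-CR. The documents do not give k. I show small values and take 4 as an illustrative upper value, because the 4 extra patients cover all dropout. It is not a firm ceiling, since 4.6.4 lets accrual rise above 30 with committee approval.

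**Step 1: reproduce the plan's table.** With x CRs in n patients the posterior is Beta(x+1, n−x+1). For 11 to 15 CRs in 26, P(rate > 40%) is 0.613, 0.750, 0.855, 0.926, 0.966. The plan prints 0.61, 0.75, 0.86, 0.92, 0.96. Agreement is within 0.01, so the prior is adequate here.

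**Step 2: direction.** If s patients are scanned, the 10.1 rate is x/s and the one-dose rate is x/(s+k). Since x/s ≥ x/(s+k), the 10.1 rate is never lower. The two are equal when k = 0 or x = 0.

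**Step 3: accrual runs to 26 scanned patients.** The one-dose denominator is 26 + k.

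| k | n dosed | 11 CRs: rate | 13 CRs: P(rate > 40%) |
|---|---|---|---|
| 0 | 26 | 42.3% | 0.855 |
| 1 | 27 | 40.7% | 0.813 |
| 2 | 28 | 39.3% | 0.766 |
| 3 | 29 | 37.9% | 0.715 |
| 4 | 30 | 36.7% | 0.660 |

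The 40% rule and the posterior rule each change from met to not met at k = 2. With 12 CRs the 40% rule still holds at k = 4 (12/30 = 40.0%). With 10 CRs it fails even at k = 0 (10/26 = 38.5%).

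**Step 4: accrual stops at 26 dosed patients.** Now 26 − k are scanned, and one unscanned patient is enough.

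- 10 CRs: 10/25 = 40.0% meets the 40% rule; 10/26 = 38.5% does not.
- 12 CRs: P(rate > 40%) is 0.801 for 12/25 and 0.750 for 12/26, on either side of 0.80.

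The CR counts at which the verdict changes therefore depend on which definition also governs the accrual target.

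**Step 5: how often the margin matters.** In the Step 3 setting, the chance of exactly 11 CRs in 26 is 0.15 at a true rate of 40% and 0.12 at 50%. A change of verdict on the 40% rule also needs k ≥ 2.

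**Step 6: counts needed on the one-dose set.**

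| n dosed | 26 | 27 | 28 | 29 | 30 |
|---|---|---|---|---|---|
| CRs for 40% rule | 11 | 11 | 12 | 12 | 12 |
| CRs for posterior rule | 13 | 13 | 14 | 14 | 15 |

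**The case against.** **The plan may have intended 10.1.** Enrolling 30 for 26 evaluable, and letting 4.6.4 add patients for efficacy, both point to an efficacy set smaller than all dosed patients. This stands in part: 4.6.4 supports supplementing early withdrawals that are not due to progression or toxicity. It does not support dropping progression and toxicity failures, which 10.1 does when they have no scan. The 4 extra patients could equally cover undosed patients.

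**The direction rests on an unwritten score.** This is correct. Counting unscanned patients as non-CR is the natural reading of the one-dose rule, but the plan does not state it. That silence is part of the defect.

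**The effect is small.** This also stands. Only the 40% criterion is a firm success rule. The Bayesian rule is optional, and the check whether 50% lies in the confidence interval carries no stated decision. Verdicts change only near the limits.

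Two stronger readings are tempting, and the documents do not support them.

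- A reader might infer that the futility decision reverses, for instance with 5 CRs in 20 dosed patients of whom 18 were scanned. Section 10.3.1 defines futility as posterior P(rate > 50%) below 10% and allows monitoring after each patient from 10 onwards. With a Beta(1,1) prior, 5/20 gives 0.013 and 5/18 gives 0.032, so both are futile. Even 6/20 (0.039) and 7/20 (0.095) are.
- A reader might infer that false-positive risk is inflated beyond the planned 10%. Suppose the one-dose rate is 20%, so that the scanned rate is 0.2 × (26+k)/26. The chance of at least 11 CRs in 26 is then 0.008 at k = 0 and 0.023 at k = 4, well under 10%.

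**Conclusion.** The conflict is real, stands in current text and concerns the primary endpoint. Three sections give two definitions, a fourth implies that some failures excluded by 10.1 are retained, and missing PET#2 has no score. If missing counts as non-CR, following 10.1 leaves the CR rate unchanged or raises it. With 26 scanned patients and two unscanned, the difference is 3.0 percentage points at 11 CRs (42.3% − 39.3%). That can change the conclusion at a few CR counts near the limits. If accrual stops at 26 dosed patients, a single unscanned patient can do so.

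These sizes rest on an assumed k, a Beta(1,1) prior and the non-CR score. If every dosed patient is scanned, the definitions agree. The futility looks need the same definition because they are counted in evaluable patients, but no reversed futility decision has been shown. This should be fixed, but it does not undermine the design.

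**What to change.** 1. Use one definition in 6.4.1, 10.1 and 10.3.1: all patients with at least one pembrolizumab dose. Delete the PET#2 condition from 10.1.
2. State that a dosed patient without PET#2, for whatever reason, counts as non-CR.
3. State in 4.6.4 whether a patient for whom another is added stays in the primary denominator. Keeping the patient in is the conservative choice.
4. Apply the success and futility rules to this set, and print the required CR counts for n = 26 to 30 as in the second table above.
5. Report two sensitivity analyses: the PET#2-scanned subset, and the set without patients supplemented under 4.6.4.

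Keeping 10.1 and making the one-dose set the sensitivity analysis would also remove the contradiction. It would leave likely treatment failures out of the primary estimate, so I prefer the change above.

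The cost is protocol wording, restated decision counts that depend on n, and a CR estimate that may be slightly lower. No treatment or assessment changes.
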